1.1 The research brief

The commissioning brief (HTA 01/10) specifies the key research question: “What is the comparative cost-effectiveness of laxatives compared with dietary and lifestyle changes in the treatment of elderly patients with chronic constipation”. Dietary interventions are to be differentiated from bulk laxatives, such as bran, and dietary and/or lifestyle changes may be compared with single laxative agents.

1.2 The research questions addressed by this study

In studies of individual behaviour change strategies, particularly those relating to dietary change and exercise¹⁻³, personalised interventions have been shown to be more effective than standard, non-customised approaches. Elements of personalisation variously include: assessment of the importance of making a behaviour change and confidence in carrying out the new behaviour, where the individual is situated in the ‘stages of change’ model⁴, motivational interviews⁵; discussion of current behaviour and of facilitators of and barriers to change; agreement of individualised goals and provision of personalised information and advice on behaviour change^{2;6;7}; and follow-up reinforcement contacts⁷. Such personalised interventions, however, are typically more resource-intensive than non-individualised approaches⁵. For these reasons, it is important to ascertain not just the effectiveness but also the cost-effectiveness of these strategies.

We therefore propose a pragmatic three-armed trial to compare laxative treatment of chronic constipation in older people with both standardised, non-personalised dietary and lifestyle advice (delivered in a single, short consultation) and personalised dietary and lifestyle advice (delivered in a long consultation – or two shorter consultations, with telephone reinforcement). Through the trial we will address the following key questions, derived from the research brief:

- What is the comparative clinical and cost-effectiveness of laxatives versus a combination of dietary and lifestyle advice?
- What is the comparative clinical and cost-effectiveness of brief, standardised, non-personalised dietary and lifestyle advice versus personalised dietary and lifestyle advice, including reinforcement?

1.2.1 Objectives

1. To investigate the clinical and cost-effectiveness of laxatives versus dietary and lifestyle advice.
2. To investigate the clinical and cost-effectiveness of standardised versus personalised dietary and lifestyle advice.

1.3 Detailed plan of investigation

1.3.1 Trial design

The trial will take the form of a prospective, pragmatic⁸, three-armed cluster randomised trial with an economic evaluation. Analysis will be on an ‘intention to treat’ basis. Participating practices will be randomised to one of three arms: (1) prescription of laxatives; (2) provision of standardised, non-personalised dietary and lifestyle advice; (3) provision of personalised dietary and lifestyle advice, with reinforcement.

A randomised controlled trial is the optimum design when evaluating behaviour change interventions. However, in this study, if the unit of randomisation was to be the individual patient, there would be a risk that health care professionals might provide elements of the dietary and lifestyle package to patients randomised to laxatives only. A solution to this problem is to ‘cluster randomise’ at the level of an entire practice, while collecting data about outcomes of care at the individual patient level. As patients within any one cluster are more likely to respond in a similar manner, such a design violates the assumption that the outcome for an individual patient is completely independent of that for any other patient. Therefore a cluster randomised design is not

as statistically efficient as a patient randomised design; it has lower statistical power than a patient-randomised trial of equivalent size⁹ and sample sizes need to be inflated to compensate for this (1.3.6).

1.3.2 Setting

General practices in England and Scotland and the homes of older people (aged 50 years and over) from these practices.

1.3.3 Health technologies being assessed

1.3.3.1 Treatment strategies at the patient level

Study participants will be randomised to one of three treatment strategies (1.3.1).

Within the laxatives arm, free choice of class of laxatives will be allowed. There is at present insufficient evidence^{10;11} of the relative superiority of one class of laxatives over another, or of combination therapies as opposed to single preparations. Free choice of laxative therapy will more closely replicate the situation which will pertain in routine clinical practice; adherence to treatment protocol is therefore expected to be better than where a change in drug is required. For similar reasons, leeway in dosage will be permitted, within dose ranges commonly used in clinical practice. To minimise the risk of prescribing sub-therapeutic doses, the intervention protocol will remind participating GPs of the therapeutic dose ranges for the available laxative preparations.

The dietary and lifestyle interventions will be informed by findings from previous trials of diet and lifestyle interventions^{1;2;6;7}. They will also draw upon theories of individual behaviour change, including the concept of self-efficacy¹² and the stages of change model⁴.

In both the standardised and personalised arms, the 'information package' will comprise practical, target-based advisory sheets on: diet – increased consumption of non-starch polysaccharides (NSP (fibre)) of both cereal and fruit and vegetable origin¹³ and of bread and bran products¹⁴; hydration¹⁵; dentition¹⁶; mobility and exercise^{17;18}; abdominal massage¹⁸; toilet habits¹⁷; what constitutes normal bowel function¹⁹; the action and potential side-effects of laxative use. Locality-specific information (e.g. details of local exercise programmes for older adults and of fruit-and-vegetable buying clubs) will be included in the package for those allocated to the personalised dietary and lifestyle intervention.

In both arms, this package will be delivered by practice or community nurses (according to local custom). Appointments will generally be offered at the surgery, though home visits will be an option where appropriate. In the standardised, non-personalised arm, there will be a single short (maximum of 10 minutes) appointment, with delivery of a standard pack of information and brief, general explanation of these information materials. In the personalised arm, there will be an initial long (30-45 minutes)⁵ appointment (though this may be undertaken in two shorter appointment should clinic time so dictate) and the technique of 'motivational interviewing' – 'a directive client-centred counselling style for eliciting behaviour change by helping clients to explore and resolve ambivalence'⁵ – will be employed. The personalised approach will include a patient-specific assessment of barriers to and facilitators of change and delivery of a personalised pack of information with individual targets. Patients in this arm will receive a follow-up motivational telephone call from the nurse at one week and one month after initial appointment.

A potential threat to patient recruitment and retention in this trial is patients' unwillingness to forego medication. For this reason, although diet and lifestyle will be the first-line treatment for patients allocated to those arms, the option of continuing laxative use (either prescribed or over-the-counter) will be available if required; the need for and use of such medication will be captured in patient diaries (1.3.5.1 and 1.3.5.3).

1.3.3.2 Training strategies for health professionals

An orientation and training programme will be developed for the practices recruited to the study. All practices will have an on-site training visit to discuss aspects of the treatment protocol and how it is to be delivered in the practice. In addition, a dietician with experience in health promotion will deliver in-practice training on how to deliver the dietary and lifestyle intervention to patients, as follows:

- Standardised dietary and lifestyle intervention – all primary health care professionals (general practitioners, practice and district nurses, health visitors) in the practice will be invited to a single, one hour session to introduce the programme and the patient pack.
- Personalised dietary and lifestyle intervention – all primary health care professionals (general practitioners, practice and district nurses, health visitors) in the practice will be invited to an initial one hour session to introduce the programme and the patient pack. Practice staff involved in delivering the intervention to patients will be invited to take part in two further 45 minute sessions on the delivery of a personalised pack and motivational interviewing techniques.

The choice of number and duration of training sessions is based on experience in other similar studies, and represents a balance between minimising the demands on busy health professionals' resources, whilst having sufficient time to motivate doctors and nurses and to equip them with the knowledge and skills required to deliver the interventions to patients. Our personal experience, reinforced by the literature²⁰, suggests that in-practice delivery of training of this nature is more cost-effective than delivery at a single, central location.

1.3.4 Target population

People aged 50 or over with chronic constipation living in private households. The choice of an age cut-off of people aged 50 or over has been made after due consideration of the morbidity statistics from general practice²¹ which show that general-practitioner consultation rates for constipation take off in the 45-64 age group and rise steadily with age. The exclusion of residents in long-term care reflects the different morbidity and life-style experience of long-term care residents. We will focus on a predominantly ambulant population able to independently attend a primary care clinic.

1.3.4.1 Inclusion criteria

The complexity of the revised Rome criteria for functional constipation²² militates against their use in screening for chronic constipation. Moreover, newly incident cases of constipation, especially amongst older adults, should be investigated to determine the underlying cause of the constipation and to eliminate more serious problems²³ before laxatives are prescribed.

This trial will therefore identify and recruit only 'prevalent' cases, defined in terms of those prescribed laxatives three or more times in the previous 12 months. Participants meeting this criterion will be identified from general practice computerised patient records using an electronic 'query' to interrogate repeat prescribing databases. It is recognised that the relapsing and remitting nature of constipation means that not all patients thus identified will be constipated (by objective or subjective criteria) at any given time. Eligible participants who have given informed consent will be invited to complete a baseline assessment during which current bowel function and perceptions of whether constipated will be elicited; these baseline data will be included as co-variables in our analysis (1.3.7).

1.3.4.2 Exclusion criteria

- Patients resident in long-term care.
- Patients with inflammatory bowel disease, intestinal obstruction/bowel strictures, known colonic carcinoma, and conditions contra-indicative to the prescription of laxative preparations²⁴.
- Inability to read and understand written treatment plans and educational material.
- Inability to complete outcome assessments, even with assistance (e.g. major cognitive impairment, lack of understanding of English).

1.3.5 Assessment of outcomes

1.3.5.1 Outcome measures

The primary outcome, and the criterion upon which the sample size calculations have been based, is patient-reported condition-specific quality of life at three months post recruitment (1.3.5.2). Our preferred measure of quality of life is the constipation-specific PAC-SYM / PAC-QOL²⁵, which has been demonstrated to have good validity and reliability. However, this measure is not utility-based. For the purposes of the economic evaluation (1.3.8), a measure of the utility placed by patients on

their health state will be required. The condition-specific measure of quality of life will therefore be supplemented by the generic, utility-based EQ-5D^{26;27}.

Secondary outcomes will include: bowel movement frequency; the presence/absence of the other Rome criteria for constipation; patients' own perceptions of whether or not they are constipated; patient satisfaction with bowel function; adverse effects of treatment; relapse / re-consultation rates; fluid and fibre intake (Table 1).

In addition, the cost implications of the condition and its treatment (e.g. GP consultations, purchase of prescribed and over-the-counter medication) will be assessed, as part of the economic evaluation (Table 2; section 1.3.8).

Table 1 Outcome measures

Primary outcome	Measurement method	When	Where
Health-related quality of life	Postal questionnaire	At three months post recruitment	Participant's home
Secondary outcomes	Measurement method	When	Where
Health-related quality of life	Postal questionnaire	At six and twelve months post recruitment	Participant's home
Number of bowel movements per week	Self-completed structured diary + Postal questionnaire	Daily for 6 months At 12 months	Participant's home
Other Rome criteria: straining at defecation, stool consistency, perceived incomplete evacuation	Self-completed structured diary + Postal questionnaire	Daily for 6 months & for 1 week at 12 months At 12 months	Participant's home
Subjective perception of whether constipated; satisfaction with bowel function	Telephone interview + Postal questionnaire	At 3 months At 6 months & 12 months	Participant's home
Adverse events: abdominal pain, nausea, bloating, flatulence, diarrhoea	Self-completed structured diary + Postal questionnaire	Daily for 6 months & for 1 week at 12 months At 12 months	Participant's home
Use of prescribed and OTC laxatives	Self-completed structured diary + Postal questionnaire	Daily for 6 months & for 1 week at 12 months At 12 months	Participant's home
Fluid and fibre intake	Self-completed structured diary + Postal questionnaire	1 day per month for 6 months At 12 months	Participant's home
Relapse rates: including repeat consultations	Self-completed structured diary; GP records	Daily for 6 months; Twelve months post recruitment	Participant's home (diary); General practices (GP records)
Personal measures of success with the management of constipation	Telephone interview	At 3 months and 6 months	Participant's home

Table 2 Measuring treatment impact

Impact	Measure	When	Where
Costs to participants of the condition and its management	Structured health diary; telephone interview; postal questionnaire	Using different methods, for six months	Participant's home
Consultation rates and laxative prescriptions	GP records	At twelve months post recruitment	General practices

1.3.5.2 Follow-up period

Maximum response to the interventions are expected within 12 weeks of initiation of treatment; this dictates that the primary outcome should be assessed at three months post recruitment. However, since a common criticism of behaviour change interventions is the lack of sustained effect, quality of life data will be collected again at six and twelve months post recruitment while symptom diaries will be completed daily for six months. Relapse rates (defined in terms of re-consultation and/or demand for further prescriptions for laxatives) will be monitored for twelve months post recruitment, through interrogation of patients' medical records. We believe that intensive follow-up of patients for six months coupled with extended monitoring of quality of life, consulting and prescribing data represents a reasonable compromise between placing excessive burden on respondents (posing threats to recruitment and retention rates) and assessing longer-term consequences of the interventions.

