1.3.5.3.5 Medical records (W^{52})

Data pertaining to consultation rates and prescription of laxatives for all study participants for the twelve months post recruitment will be abstracted from medical records. This will be done practice-by-practice at the end of the data collection period. Trained research nurses will interrogate paper-based and computerised records and will enter data directly to a database on lap-top computer. The electronic query used to identify patients at the beginning of the trial will be adapted to capture data on laxative prescriptions. We have used these methods of data collection to good effect in previous similar studies.

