1.3.5.4 Participants' pathways through trial

		Activity
1		Potential participants identified from computerised practice databases using simple electronic query to flag individuals receiving prescriptions for constipation (3 or more in previous 12 months).
2		Initial screen by practice to identify clear exclusions.
3		Written invitation sent by practice (facilitated by research team) to patient to participate in study. Contact details form and pre-paid envelope included for patients wishing to join the study included. Research team to contact patient to answer questions and explain about process for informed consent. Consent form posted to patient with pre-paid envelope. Self completion questionnaire and pre-paid envelope also sent. Control patients will receive their diary (including pre-paid envelope) at this point.
4	W^0	When consent form is returned the telephone baseline interview will be conducted. patient advised to expect contact from practice to arrange 'intervention start' appointment.
5	W^1	Appointment at practice – laxative prescription issued or diet and lifestyle intervention initiated. All patient information and baseline data destroyed by research team if patient notifies practice of their wish to withdraw from study.
6	W^2	One week reinforcement phone call from nurse to patients randomised to personalised diet and lifestyle advice
7	W^{3-4}	Intervention fidelity measure – a small sample of patients in the standardised and personalised intervention arms of the trial will receive a short postal questionnaire to ask about the diet and lifestyle advice.
8	W^5	One month reinforcement phone call from nurse to patients randomised to personalised diet and lifestyle advice
9	W^{12}	Three month follow up outcome assessment (postal questionnaire) and collection of cost data and personal levels of success (telephone interview)
10	W^{26}	Six month follow up outcome assessment (postal questionnaire) and collection of cost data and personal levels of success (telephone interview)
11	W^{52}	Twelve month follow up outcome assessment (postal questionnaire & 1-week symptom diary). Review of practice notes to abstract data on consultation rates and prescription patterns.

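### Relapse counts further laxative prescriptions, which in the laxative arm renew the allocated treatment, so laxatives versus advice on this secondary outcome is biased against laxatives

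*Protocol*

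**What the plan says.** Section 1.3.5.2 gives one definition of relapse for all arms: "Relapse rates (defined in terms of re-consultation and/or demand for further prescriptions for laxatives) will be monitored for twelve months post recruitment". The source named there is the patients' medical records. Section 1.3.5.3.5 describes the abstraction: "Data pertaining to consultation rates and prescription of laxatives for all study participants for the twelve months post recruitment will be abstracted from medical records". Table 1 lists relapse as a secondary outcome, with the diary and the GP records as its two sources.

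Section 1.3.1 lists the arms as "1) prescription of laxatives; (2) provision of standardised, non-personalised dietary and lifestyle advice; (3) provision of personalised dietary and lifestyle advice, with reinforcement". In the patient pathway (1.3.5.4), the W1 appointment is where treatment starts: "laxative prescription issued or diet and lifestyle intervention initiated". Section 1.3.4.1 restricts entry to prevalent cases, "defined in terms of those prescribed laxatives three or more times in the previous 12 months", found by searching repeat-prescribing databases.

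In the two advice arms, section 1.3.3.1 makes diet and lifestyle the first-line treatment and keeps laxatives available if the patient needs them. Section 1.3.6.4 calls this rescue medication.

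**The concern.** One component of the outcome is the treatment that one arm is assigned to receive. In the laxative arm a further prescription is adherence. In the advice arms it is at least a departure from the first-line plan, and possibly a failure of it. The same recorded event therefore means different things by arm, and neither a return of symptoms nor a preceding remission is required before it counts.

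At stake is Objective 1, laxatives versus advice, on the outcome that section 1.3.5.2 ties to whether effects last. A higher relapse rate in the laxative arm could be read as poorer durability when it shows only that patients kept collecting what they were allocated. Adjustment for baseline, as section 1.3.7 plans, cannot remove this, because the treatment is built into the outcome itself.

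**Working it through.** The protocol states no relapse rate, so there is no figure of its own to reproduce. The check sets the sections side by side, then asks what the size depends on.

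**1. What triggers the event.** The two components are joined by *and/or* (1.3.5.2). A further laxative prescription is sufficient without any consultation about symptoms.

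**2. What a stable laxative-arm patient does.** Take the minimum entry rate of 3 prescriptions in 12 months (1.3.4.1) and suppose it continues. One is the W1 prescription (1.3.5.4), which the word *further* can exclude. That leaves 3 − 1 = 2 further prescriptions. This patient meets the definition twice with no change in bowel function.

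**3. What the same event means in the advice arms.** Diet and lifestyle comes first and laxatives follow if required (1.3.3.1), so a further prescription is not the allocated treatment.

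**4. Whether another section repairs it.**
- Table 1 adds the diary as a source but does not change the definition.
- Section 1.3.7 models 12-month consultation and prescription rates with arm as a fixed effect and states no arm-specific handling.
- Section 1.3.4.1 itself accepts that not everyone found through prescriptions is constipated at a given time. A prescription therefore does not establish current constipation.

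**5. What the size depends on.** Let c be the proportion with a genuine, symptom-driven relapse, equal in all arms. Among the rest, let f_L (laxatives) and f_D (advice) be the proportions who obtain a further prescription while well.

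- Recorded relapse in an arm: p = c + (1 − c) × f
- Spurious difference: p_L − p_D = (1 − c) × (f_L − f_D)

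The protocol gives none of c, f_L or f_D. The values below are assumptions that show only the range:

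| Assumed p_L | Assumed p_D | Spurious difference |
|---|---|---|
| 100% | 30% | 70 points |
| 100% | 60% | 40 points |
| 90% | 80% | 10 points |
| 90% | 90% | 0 points |

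**6. Whether a small artefact would matter.** Take 19 practices of 25 patients per arm and an ICC of 0.04 (1.3.6.3). That ICC was set for quality of life and is borrowed here as an assumption.

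- Design effect: 1 + 24 × 0.04 = 1.96
- Effective number per arm: 475 / 1.96 = 242.3
- For 90% versus 80%, the standard error under no difference is √(2 × 0.85 × 0.15 / 242.3) = 0.0324, and under the difference √((0.09 + 0.16) / 242.3) = 0.0321
- z = (0.10 − 1.96 × 0.0324) / 0.0321 = 1.13, so the probability of a significant result at two-sided 5% is about 87%

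Under these assumptions, even a 10-point artefact would usually be declared a difference between arms.

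**The case against.** The strongest reply has five parts.

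- **Renewal is not certain.** The word *further* can leave out the W1 prescription, and the protocol describes constipation as relapsing and remitting. A laxative-arm patient who neither renews nor re-consults is not counted. This stands. A reader might infer that the whole laxative arm relapses by definition, but the text does not support that.
- **Advice-arm patients may renew too.** They entered on the same prescribing criterion and may continue prescribed laxatives. This also stands. A reader might infer a gap of 40 to 70 points, but those figures rest on assumed rates, and the gap could be much smaller or near zero.
- **Symptoms and prescriptions are already reported elsewhere.** Table 1 has its own rows for symptoms, perceived constipation and laxative use, Table 2 lists prescriptions, and section 1.3.7 names consultation and prescription rates rather than a relapse composite. This limits the damage and makes the fix cheap. It does not make relapse, as section 1.3.5.2 words it, interpretable.
- **The analysis plan could settle it.** How the diary feeds into relapse could be left there. The definition has not been left open, because the protocol fixes it in words.
- **Scheduled contacts.** A reader might infer that protocol visits will also be counted as re-consultations, since the long appointment in the personalised arm may be split: "though this may be undertaken in two shorter appointment should clinic time so dictate". No section says they will be counted. If they were, relapse would rise in the personalised arm, which works against the bias described here. It is a reason to record the distinction, not part of the finding.

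**Conclusion.** The point holds as a fault in the stated definition of one secondary outcome. Followed as written, relapse counts continued allocated treatment in arm 1 and a departure from first-line treatment in arms 2 and 3, so it cannot be compared between laxatives and advice. The direction is against laxatives, provided that patients who are well renew more often in the laxative arm than in the advice arms, as the allocation implies. The document supports that direction but no particular size.

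Quality of life at three months and the 57-practice calculation do not use relapse. The prescription component has the same meaning in both advice arms, so Objective 2 does not carry this asymmetry.

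**What to change.** Reconcile section 1.3.5.2 with sections 1.3.1, 1.3.3.1, 1.3.5.4 and Table 1. Define relapse identically in all three arms from data the trial already collects:

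- return of constipation on the Rome items of the diary or questionnaire, or by the patient's own perception; and/or
- a constipation-related consultation that is not a contact scheduled by the protocol.

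Report laxative prescriptions only as treatment use and resource use, for which Tables 1 and 2 already provide.

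The cost is a rewording and one scheduled/unscheduled field on the record-abstraction form, which should be in place before abstraction starts because the two kinds of contact may not be separable later. The symptom part becomes sparser after month six, when the daily diary ends and only the 12-month questionnaire and the one-week diary remain. The protocol should state that limit.

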1.3.5.3.2 Health diary (daily for 6 months from W⁰)

To minimise recall bias, data on bowel function (based on the Rome criteria)²², fluid and fibre intake, perceptions of whether constipated and use of laxatives will be gathered by a structured (tick box format) health diary, completed each day and returned monthly for six months.

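### Relapse does not mean the same thing in each arm: permitted over-the-counter laxatives go uncounted, while the laxative arm's allocated prescriptions can count

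*Protocol*

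**What the plan says.** Protocol 1.3.5.2 (Follow-up period) gives the only definition of relapse: "Relapse rates (defined in terms of re-consultation and/or demand for further prescriptions for laxatives) will be monitored for twelve months post recruitment". It names one source: "through interrogation of patients' medical records". Section 1.3.5.3.5 describes that abstraction as "Data pertaining to consultation rates and prescription of laxatives for all study participants for the twelve months post recruitment"; purchased laxatives are not part of it.

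Table 1 in 1.3.5.1 lists the same outcome with two sources: "Relapse rates: including repeat consultations Self-completed structured diary; GP records". The diary runs daily for six months and the records are read at twelve months. Section 1.3.5.3.2 describes the diary content: "perceptions of whether constipated and use of laxatives will be gathered by a structured (tick box format) health diary", together with bowel function and fluid and fibre intake. Consultations are not among the items listed there.

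For the two advice arms, 1.3.3.1 says that "the option of continuing laxative use (either prescribed or over-the-counter) will be available if required" and that "the need for and use of such medication will be captured in patient diaries". Table 1 also has a separate secondary outcome, "Use of prescribed and OTC laxatives", measured by daily diary for six months, a one-week diary at 12 months and a postal questionnaire at 12 months.

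In the laxative arm, the first practice appointment in the pathway (1.3.5.4) consists of issuing a laxative prescription.

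**The concern.** An outcome compared between arms has to record the same event in each arm. This one does not, for two reasons.

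First, the advice arms have an expressly permitted route back to laxatives, or of staying on them, that leaves no trace in the GP record. A patient who uses only that route meets neither part of the definition.

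Second, in the laxative arm a further prescription may be nothing more than the allocated treatment carried on, yet the definition counts it as relapse.

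Both features would tend to make advice look better. What is at stake is the reading of a named secondary outcome and of the twelve-month prescription rates, which 1.3.7 plans to model. A lower rate under advice could partly reflect a move from prescription to purchase, or the fact that the comparator is supplied by prescription.

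**Working it through.** The protocol gives no relapse rate, no share of patients who only buy laxatives, and no power for relapse, so there is no figure to reproduce. The check is of the text, followed by an illustration on assumed values.

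**Step 1: apply the 1.3.5.2 definition to four patients.**

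| Patient | Entry in GP record | Score |
|---|---|---|
| Advice arm, obtains a prescribed laxative | Prescription | Relapsed |
| Advice arm, relies on purchased laxatives, does not consult | None | Not relapsed |
| Laxative arm, bowel function satisfactory, collects another prescription of the allocated treatment | Prescription | Relapsed, on a plain reading |
| Laxative arm, only buys laxatives, does not consult or ask for a prescription | None | Not relapsed |

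The second and third rows are the problem. The fourth shows that purchase can go unseen in the laxative arm too.

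**Step 2: what is collected on purchased laxatives, by period.**
- Months 0-6: the daily diary records laxative use, and telephone interviews at W13 and W26 ask about purchases for costing (1.3.5.3.4).
- Months 7-12: the one-week diary and the postal questionnaire at 12 months (Table 1). Participant costs are collected for six months only (Table 2). The questionnaire content listed in 1.3.5.3.3 does not mention laxative use, although Table 1 promises it at 12 months.

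The data for months 0-6 therefore exist; coverage in months 7-12 is thin.

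**Step 3: illustration of the first feature.** Let R be true relapse, assumed to be 40% in every arm, and let a be the assumed share of advice-arm relapses that are by purchase alone. Assume no such share in the laxative arm. Recorded advice-arm relapse = R × (1 − a).

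| a | Recorded, advice | Recorded, laxative | Ratio |
|---|---|---|---|
| 10% | 0.40 × 0.90 = 36% | 40% | 0.90 |
| 25% | 0.40 × 0.75 = 30% | 40% | 0.75 |
| 50% | 0.40 × 0.50 = 20% | 40% | 0.50 |

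If the share is equal in all arms, the ratio is 1.00. If it is 10% in the advice arms and 25% in the laxative arm, the ratio is 36% / 30% = 1.20. The direction depends on which arm buys more.

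**Step 4: scale against sampling error.** From 1.3.6.3, 19 practices × 25 patients = 475 per arm, and the design effect is 1 + 24 × 0.04 = 1.96. At a proportion of 0.5, which gives the largest variance, SE of a difference = sqrt(2 × 0.25 / (475 / 1.96)) = 0.0454, or about 4.5 points. The shortfalls of 4, 10 and 20 points in step 3 are then about 0.9, 2.2 and 4.4 standard errors. This is only a yardstick: the intra-class correlation is the one assumed for quality of life, and the records cover all participants, not only the 25 per practice expected to give follow-up data.

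**Step 5: illustration of the second feature.** Let c be the assumed share of non-relapsed laxative-arm patients who receive a further prescription as continued treatment. Recorded laxative-arm relapse = R + (1 − R) × c. With R = 40% and c = 10%, 25% or 50%, this is 0.40 + 0.60 × c = 46%, 55% or 70%. This inflation does not depend on purchasing, and the protocol contains nothing that excludes it.

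**The case against.** The strongest reply is that the protocol does not ignore purchased laxatives. Table 1 names the diary as a relapse source for six months, and the diary records laxative use. Use of prescribed and purchased laxatives is a secondary outcome in its own right, so a shift from one to the other would be visible beside the relapse rate. This stands. A reader might infer that purchased use is lost, or that relapse is read from records alone throughout; the documents do not support either. What they show is a conflict between Table 1 and 1.3.5.2 over the source. Table 1 does not resolve it, because it does not say that a diary entry of purchased laxatives counts as relapse, and the 1.3.5.2 definition says otherwise.

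A reader might also infer that relapse is misclassified in favour of advice by a known amount. That is not established. The direction rests on purchase-only use being more common under advice. This is plausible because the laxative arm is supplied by prescription, but no section gives a figure, and every participant entered as an established prescription user (1.3.4.1).

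Nor is relapse the main test of lasting effect. Section 1.3.5.2 answers that criticism with quality of life at six and twelve months and six months of diaries, and defends lighter later follow-up on grounds of respondent burden. Records have real merits: they cover all participants and avoid recall and diary gaps. As a measure of service demand the definition is reasonable, and 1.3.5.1 itself pairs relapse with re-consultation.

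An analysis plan may say how two sources are combined. It would still inherit a definition that the protocol has fixed and that reads differently by arm.

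**Conclusion.** The concern holds as a flaw in the definition of one secondary outcome. Followed as written, 1.3.5.2 scores an advice-arm patient who uses only purchased laxatives as not relapsed, and can score a laxative-arm patient who continues allocated treatment as relapsed. The comparison of relapse between the laxative arm and the advice arms is therefore not interpretable as relapse. Both features probably favour advice. The size is unknown: the figures above rest on an assumed 40% true relapse and assumed shares of 10% to 50%, and the first feature vanishes if purchase-only use is equal across arms.

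It is tempting to conclude that any laxative use, bought or prescribed, should count as relapse in every arm. That would make the second feature worse, because compliant laxative-arm patients would be scored as relapsed. The primary outcome and the sample size are not affected.

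**What to change.** 1. Reconcile Table 1 with 1.3.5.2: state one source or combination of sources for relapse, and what the diary contributes.
2. Report the records-only measure as NHS consultation and prescription demand, not as relapse.
3. For the comparison of the two advice arms in months 0-6, count diary-recorded purchased as well as prescribed laxatives. Because 1.3.3.1 speaks of continuing use, state how a patient who never stopped is scored.
4. For comparisons with the laxative arm, use a definition that does not count continued allocated treatment, for example one built on the symptom and perceived-constipation diary data already collected. Interpret prescription rates alongside the separate outcome on prescribed and purchased laxatives.
5. Make the laxative-use item that Table 1 promises at 12 months cover purchases since month 6, and list it in 1.3.5.3.3.

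The cost is a revised definition, a relabelled table row and the wording of one questionnaire item. The downside is that part of the outcome becomes self-reported, with missing diary data and, for months 7-12, recall over half a year. Keeping the records measure as a separate result preserves its complete coverage.
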